### **6.3 Sample Size and Power**

Quadriceps function is the primary outcome for this investigation, as it is the critical factor in controlling impulsive knee joint loading linked to development of post-traumatic knee OA. We conducted *a priori* power analyses using data from our preliminary investigation involving these same vibratory stimuli following experimental knee joint effusion. Pre-post change scores were calculated as described above in the statistical methods for Specific Aim 1, and effect size indices were calculated for one-way ANCOVA using pre-test scores as the covariate. These analyses indicate that a sample of 45-63 subjects (15-21 per group) would provide statistical power of 0.80 for  $\alpha = 0.05$  to identify significant overall ANCOVA models for CAR ( $f = 0.48$ ) and peak torque ( $f = 0.41$ ), where  $f$  is the effect size calculated as the square root of the ratio of the between-group sum of squares and the error sum of squares. Further, these preliminary data generated the pairwise effect sizes presented in the table below calculated using the following equation:

$$\text{Effect Size} = \frac{[\Delta\text{WBV} \text{ (or } \Delta\text{LMV} \text{ )} - \Delta\text{Control}]}{\text{Pooled Standard Deviation}}$$

Effect Sizes for *Post Hoc* Group Comparisons of Pre-Post Change Scores

Quadriceps Function Variable	WBV vs. Control	LMV vs. Control	LMV vs. WBV
CAR	0.84	0.78	0.36
Peak Torque	0.98	0.70	0.35

Statistical power for the effect sizes given in Table 2 was calculated for one-tailed independent t-tests. These estimates indicate that a sample of 39-78 subjects (13-26 per group) would provide statistical power of 0.80 for  $\alpha = 0.05$  to evaluate pairwise comparisons between the Control group and each vibratory intervention (i.e. Aim 1). In contrast, 194 subjects (97 per group) would be necessary to provide adequate power to identify the relatively small effect sizes for comparing the two vibratory interventions (i.e. Aim 2). The associated mean differences in CAR between WBV and Control and between LMV and Control were 8.26% and 5.86%, respectively, while the difference between LMV and WBV was only 0.68%. Similarly, the associated mean differences in peak torque between WBV and Control and between LMV and Control were 0.29 N/kg and 0.20 N/kg respectively, while the difference between LMV and WBV was only 0.04 N/kg. These data suggest that the small mean differences in the dependent variables between WBV and LMV, even when powered sufficiently, are not likely clinically or physiologically relevant. Therefore, we will recruit a sample of 75 individuals (25 per group) to address the proposed specific aims. This sample size will provide adequate power to demonstrate similar improvements in quadriceps function with WBV and LMV.

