2. **WBV and LMV enhance quadriceps function similarly in individuals with simulated knee trauma.** We evaluated the effects of WBV and LMV on quadriceps function in healthy individuals with simulated knee trauma (n=43). The underlying cause of quadriceps dysfunction, AMI, is attributable to sensory information that signals pathology including pain, inflammation, swelling, and damage to mechanoreceptors. AMI can also be induced experimentally by injecting saline into the knee joint which mimics the effects of swelling/effusion. Quadriceps function was assessed via the central activation ratio (CAR). CAR quantifies an individual’s ability to voluntarily activate a muscle, and is an indicator of AMI. A detailed description of this method is provided in the RESEARCH STRATEGY below. Following pre-test measures, 60mL of saline was injected into the knee joint space to induce AMI. Subjects were then exposed to WBV, LMV, or no vibration (Control), and quadriceps function was reassessed post-intervention. The interventions and methods for assessing quadriceps function utilized in this preliminary study are identical to those proposed in the RESEARCH STRATEGY. CAR improved significantly with WBV (+8.3%) and LMV (+5.9%), but not in the Control group (+0.7%). While both forms of vibration improved quadriceps function, this improvement did not differ between LMV and WBV. Additionally, subjects who experienced the greatest inhibitory effects of effusion displayed the greatest improvements in quadriceps function with vibratory stimuli. *These findings support our hypothesis that WBV and LMV may enhance quadriceps function similarly in individuals with knee pathology.* We

anticipate that individuals with “real” knee pathologies (as opposed to the acute, simulated trauma in this preliminary investigation) will realize substantially larger improvements in quadriceps function due to the chronic nature of their quadriceps dysfunction.

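### In section 6.3 the CAR effect size of 0.84 for WBV versus Control does not fit the other CAR planning figures, and the CAR mean differences quoted there are mislabelled

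*Combined protocol and SAP*

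**What the plan says.** Section 6.3 names quadriceps function as the primary outcome and plans from a pilot study of experimental knee effusion. For the overall ANCOVA it uses f = 0.48 (CAR) and f = 0.41 (peak torque), with the pre-test score as covariate, and concludes that "a sample of 45-63 subjects (15-21 per group) would provide statistical power of 0.80".

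A table headed as effect sizes for post hoc "Group Comparisons of Pre-Post Change Scores" follows, with columns WBV vs Control, LMV vs Control and LMV vs WBV. Its rows read "CAR 0.84 0.78 0.36" and "Peak Torque 0.98 0.70 0.35". The denominator is given only as "Pooled Standard Deviation"; the text does not say whether it is shared by all three arms or formed separately for each pair. From this table, with one-tailed t-tests, the section states for the Control comparisons that "a sample of 39-78 subjects (13-26 per group) would provide statistical power of 0.80".

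Section 6.3 then reports CAR mean differences of 8.26 (WBV vs Control), 5.86 (LMV vs Control) and 0.68 (LMV vs WBV). Section 1.4 describes the pilot in "healthy individuals with simulated knee trauma (n=43" in total) and reports its changes arm by arm, in per cent: "CAR improved significantly with WBV (+8.3%) and LMV (+5.9%), but not in the Control group (+0.7").

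**The concern.** Effect sizes that share one SD must add up: WBV vs Control should equal LMV vs Control plus the WBV-LMV gap. For CAR, 0.78 + 0.36 = 1.14 (1.13 to 1.15 allowing for rounding), but the table prints 0.84. The planned ANCOVA with Dunnett comparisons (section 6.2) uses one error SD for all three arms, so that is the natural scale for planning.

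CAR is a measure of the primary outcome. If 0.84 is the wrong figure, the plan understates its power for WBV vs Control and little else changes. If the SD behind 0.84 is the right one, f and the LMV effect size are both too large, and the CAR requirement for the overall test exceeds the planned 75.

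**Working it through.** **Inputs.** Arm changes in CAR (section 1.4): WBV 8.3, LMV 5.9, Control 0.7. The differences are 7.6 (WBV-Control), 5.2 (LMV-Control) and 2.4 (WBV-LMV). Effect sizes 0.84, 0.78, 0.36 and f = 0.48 (section 6.3). Pilot n = 43 (section 1.4). Alpha 0.05, power 0.80, three equal groups.

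**1. Reproducing the plan's figures.** Noncentral F with noncentrality N × f²: f = 0.48 gives 45 (power 0.800; 48 if the covariate degree of freedom is counted, because power at 45 is then 0.7997), and f = 0.41 gives 63. So 45-63 follows from the printed f values. One-tailed t: d = 0.70 gives 26 per group; d = 0.98 gives 13 by the normal approximation or 14 by noncentral t. Both ends of 13-26 therefore come from peak torque.

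**2. SD implied by each CAR figure.** For a pair, SD = mean difference / d. For f, SD = (SD of the three arm means, divisor 3) / f. The mean of the arms is 4.97, and the SD of the means is √[(3.33² + 0.93² + 4.27²)/3] = 3.17.

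| Figure | Calculation | Implied SD |
|---|---|---|
| LMV vs Control, 0.78 | 5.2 / 0.78 | 6.67 |
| LMV vs WBV, 0.36 | 2.4 / 0.36 | 6.67 |
| f = 0.48 | 3.17 / 0.48 | 6.61 |
| WBV vs Control, 0.84 | 7.6 / 0.84 | 9.05 |

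Section 6.3 defines f from sample sums of squares. With n = 43 that multiplies the third SD by √(43/40), giving 6.85. Either way, 0.84 is the outlier.

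**3. If the SD is about 6.67.** WBV vs Control is 7.6 / 6.67 = 1.14, and f is 3.17 / 6.67 = 0.476, close to the stated 0.48. One-tailed t: 1.14 needs 11 per group (10 by the normal approximation), against 19 for 0.84. The lower end of 13-26 falls to about 11; the upper end and 45-63 do not move.

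**4. If the SD is about 9.05.** LMV vs Control is 5.2 / 9.05 = 0.57, LMV vs WBV is 2.4 / 9.05 = 0.27, and f is 3.17 / 9.05 = 0.35. The overall test needs 84 subjects, and power at 75 is about 0.76. With the √(43/40) factor, f is 0.36, the requirement is 78 and power at 75 is about 0.79. LMV vs Control needs 39 per group one-tailed, and its power at 25 per group is about 0.64.

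**5. Separate pooled SDs for each pair.** With equal arms (assumed), each pair's squared SD is the mean of its two arm variances. Solving 9.05² = (W + C)/2, 6.67² = (L + C)/2 and 6.67² = (W + L)/2 gives arm SDs of about 9.05 (WBV), 2.65 (LMV) and 9.05 (Control), a variance ratio near 12:1. The average SD is √[(81.9 + 7.0 + 81.9)/3] = 7.54, so unadjusted f is 3.17 / 7.54 = 0.42. Reaching 0.48 then requires the pre-test to explain 1 − (0.42/0.48)², about 23%, of the variance of change.

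**6. The mean-difference labels.** If 8.26 and 5.86 were both differences from Control, LMV vs WBV would be 8.26 − 5.86 = 2.40, not 0.68. The three values round to the within-arm changes of 8.3, 5.9 and 0.7 in section 1.4, so 0.68 appears to be the Control change. Steps 2 to 5 use that reading. Taking 8.26 and 5.86 literally as differences from Control gives SDs of 9.83 (0.84), 7.51 (0.78), 6.67 (0.36, using 2.40) and 7.23 (f), and 0.84 remains the outlier. With 0.68 as the LMV-WBV difference, 0.36 implies an SD of 1.89, and no set of arm SDs fits (equal arms).

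**The case against.** The strongest reply is that section 6.3 never says one SD was used. The table is for two-group comparisons powered as independent t-tests, which ordinarily pool only the two arms compared, and effect sizes on different SDs need not add up. That stands as a reading of the text. It is why a reader should not infer that some CAR figure must be wrong whichever one is trusted: that holds only under a common SD. But for CAR this reading requires the very unequal SDs in step 5, plus a covariate gain in f. The documents report neither, and such a spread would conflict with the equal-variance t and F calculations.

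A reader might also see the same fault in the peak-torque row, because 0.98 − 0.35 = 0.63 rather than 0.70, and conclude that the 26 per group should be 32. The documents do not support this. Reading 0.29, 0.20 and 0.04 as arm changes, as for CAR, pair-specific pooling fits that row with ordinary arm SDs of about 0.28, 0.23 and 0.23.

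A third tempting step is to keep both 0.84 and 0.78 on one SD, which gives f = 0.38 and a requirement of 69. That contradicts the pilot means: the two effect sizes have a ratio of 1.08, whereas the differences from Control have a ratio of 7.6/5.2 = 1.46.

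Finally, it is fair to say that the practical effect is small in the likelier case, since 0.84 sets neither end of 13-26.

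**Conclusion.** The CAR planning row is not coherent on the common SD that the planned analysis assumes. Three of the four CAR figures agree on an SD of about 6.6 to 6.7, and 0.84 stands about 36% away (9.05 / 6.67 = 1.36). The likelier error is therefore 0.84 itself, which understates the planned power for WBV vs Control. The less likely case, SD about 9, is the one with consequences: about 84 subjects for the overall test on CAR, and a materially weaker LMV comparison.

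This rests on the section 1.4 arm changes, on a common SD, and on reading 8.26, 5.86 and 0.68 as within-arm changes. The mislabelling of those three values does not depend on any assumed SD. It also matters because section 6.3 uses the 0.68 to argue that the LMV-WBV difference is unlikely to be relevant.

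A reader might infer that 45-63 is wrong or that 75 is too few. Neither is shown: 45-63 reproduces from the printed f values and fails only if the larger SD is correct. Without the pilot SDs, the documents cannot decide between the two cases.

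**What to change.** From the pilot data, recompute the three CAR effect sizes and f with the error SD of the three-arm ANCOVA, and state in section 6.3 which SD is used. Replace whichever figure proves wrong. Restate 13-26 per group, and 45-63 if f changes, and give the resulting power at 75 subjects. In the same edit, relabel 8.26, 5.86 and 0.68, give the actual between-group CAR differences, and check the peak-torque differences in the next sentence, where 0.29 − 0.20 = 0.09 but 0.04 is printed. If the pilot arm SDs really are as unequal as step 5 requires, say so and explain how the equal-variance planning allows for it.

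The cost is a short rerun on data that the sponsor should hold and a wording change in one section. The sample size stays at 75.

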### **6.2 Statistical Methods**

**Specific Aim 1: To determine the effects of WBV and LMV on quadriceps function, proprioception, and gait biomechanics in individuals with ACLR.**

Analyses for Aim 1 will be performed using pre-post change scores for quadriceps function, proprioception, and gait biomechanics as dependent variables in separate statistical models. Mean change scores will be compared across groups (WBV, LMV, and Control) via one-way analysis of covariance (ANCOVA). Dunnett's procedure will be used to evaluate each the least-squares means for each of the intervention arms (WBV and LMV) versus control in a relatively powerful manner while controlling the overall significance level at two-sided 0.05. The corresponding pre-test values for each dependent variable will be managed as a covariate in these models to increase precision of the treatment effects, as well as to account any random imbalances among the groups with respect to these pre-scores. Other covariates would include variables with random imbalances across the groups measured at the pre-test.

The number of individuals who display HST prior to and following the intervention (or control) will be compared via McNemar's test. This analysis produces a  $\chi^2$  statistic for paired samples (i.e., the proportion with HST at pre-test vs. post-test, separately for each group).

**Specific Aim 2: To compare the effects of WBV and LMV on quadriceps function, proprioception, and gait biomechanics in individuals with ACLR.**

Aim 2 will be evaluated using the statistical models described above for Aim 1, but with focus on the statistical contrast of WBV versus LMV. Specifically, the pre-post change scores for each dependent

variable, adjusted for covariates, will be tested for the pairwise comparison of WBV versus LMV at the two-sided 0.05 significance level.

**Specific Aim 3: To identify factors that predict the effects of LMV and WBV on quadriceps function, proprioception, and gait biomechanics in individuals with ACLR.**

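### Aim 1 power of 0.80 was computed for one-tailed t-tests, but the planned test is a two-sided Dunnett comparison: at 25 per group, power for LMV peak torque is about 0.59

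*Combined protocol and SAP*

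**What the plan says.** Section 6.2, Specific Aim 1, compares mean pre-post change across WBV, LMV and Control by ANCOVA with the pre-test value as covariate. For the arm-level question, "Dunnett's procedure will be used to evaluate each the least-squares means for each of the intervention arms (WBV and LMV) versus control", with the overall level held at two-sided 0.05.

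Section 6.3 makes quadriceps function the primary outcome and gives pilot effect sizes for two measures, in the order WBV vs Control, LMV vs Control, LMV vs WBV: "CAR 0.84 0.78 0.36" and "Peak Torque 0.98 0.70 0.35". It then says "Statistical power for the effect sizes given in Table 2 was calculated for one-tailed independent t-tests", and concludes for the comparisons with Control that "a sample of 39-78 subjects (13-26 per group) would provide statistical power of 0.80" at alpha 0.05. The decision follows: "Therefore, we will recruit a sample of 75 individuals (25 per group) to address the proposed specific aims".

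Section 6.3 also sizes the overall ANCOVA test (45 to 63 subjects in total). No section gives power for the two-sided Dunnett comparisons.

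**The concern.** The power statement and the analysis plan describe different tests of the same contrasts. The sizing test is one-tailed and takes no account of there being two comparisons with Control. The planned test is two-sided and adjusts for both. Each difference makes the stated power too high for the test that will be run.

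Aim 1 is the main efficacy question. The comparison hit hardest is LMV on peak torque, the quadriceps measure named in the synopsis. Section 1.3 presents LMV as portable, cheaper and possibly more effective. If true effects equal the assumed ones, a significant WBV result beside a non-significant LMV result would be a common chance pattern. A reader who believes power was 0.80 could take it as evidence that LMV does not work.

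**Working it through.** **Inputs.** Effect sizes d against Control (section 6.3): peak torque 0.98 (WBV) and 0.70 (LMV); CAR 0.84 (WBV) and 0.78 (LMV). n = 25 per group in three equal groups (sections 3.2 and 6.3). Planned level: two-sided 0.05 overall, two comparisons sharing one control (section 6.2). Assumption: the tabled d applies to the planned analysis with no further covariate gain.

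**Step 1: reproduce the plan's range.** The table gives the n per group for 0.80 power with an unadjusted t-test at 0.05, by the exact noncentral t with noncentrality d·√(n/2) and 2n − 2 df. Normal-approximation values are in brackets.

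| d | one-tailed | two-sided |
|---|---|---|
| 0.98 | 14 (13) | 18 (17) |
| 0.84 | 19 (18) | 24 (23) |
| 0.78 | 22 (21) | 27 (26) |
| 0.70 | 26 (26) | 34 (33) |

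The stated 13 to 26 appears only in the one-tailed column; the lower end, 13, is the normal approximation. The upper end is one more than the 25 per group enrolled: 3 × 26 = 78 against 75. The 97 per group that section 6.3 quotes for Aim 2 is likewise the one-tailed result, at d = 0.36. The two-sided test of section 6.2 would need 123.

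**Step 2: critical value of the planned test.** Residual df = 75 − 3 groups − 1 covariate = 71. With two comparisons, correlation 0.5 and overall two-sided 0.05, numerical integration gives c = 2.257. The one-tailed t-test at 48 df has 1.677.

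**Step 3: power at 25 per group.** Noncentrality is δ = d·√(25/2) = 3.536·d, and power = P(|T| > c), where T is noncentral t.

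| Comparison | d | δ | one-tailed t | two-sided t | two-sided Dunnett |
|---|---|---|---|---|---|
| WBV, peak torque | 0.98 | 3.465 | 0.96 | 0.92 | **0.88** |
| WBV, CAR | 0.84 | 2.970 | 0.90 | 0.83 | **0.76** |
| LMV, CAR | 0.78 | 2.758 | 0.86 | 0.77 | **0.69** |
| LMV, peak torque | 0.70 | 2.475 | 0.79 | 0.68 | **0.59** |

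By simulation of 400,000 trials, both arms beat Control in 0.56 (peak torque) and 0.59 (CAR) of trials. At least one arm does so in 0.91 and 0.86. For peak torque, WBV alone is significant in 0.32.

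**Step 4: n per group for 0.80 under Dunnett.** 21 (d = 0.98), 28 (0.84), 32 (0.78) and 39 (0.70; power 0.801).

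**Step 5: effect of the covariate.** If the pre-test correlates r with the change score and the tabled SD is unadjusted, d becomes d/√(1 − r²). For LMV peak torque, r = 0.3, 0.4, 0.5 and 0.6 give power 0.63, 0.67, 0.73 and 0.80. Power of 0.80 at n = 25 needs d = 0.878, so r² = 1 − (0.70/0.878)² ≈ 0.36 and r ≈ 0.60. The same calculation gives r² ≈ 0.21 for LMV CAR and 0.09 for WBV CAR.

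**Step 6: does section 6.3 show such a gain?** For peak torque, take the group effects as 0, 0.70 and 0.98, with mean 0.56. Then f = √[(0.56² + 0.14² + 0.42²)/3] = √0.170 = 0.41. The stated ANCOVA f is also 0.41, so no gain is visible. For CAR, the effects 0, 0.78 and 0.84 give f = √[(0.54² + 0.24² + 0.30²)/3] = √0.146 = 0.38, against a stated 0.48. Some gain is possible there. Its size is uncertain, because the SDs are not reported and other reconstructions put the unadjusted f anywhere from about 0.35 to 0.46.

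**The case against.** Several points on the other side are fair.

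- **The basis is disclosed.** Section 6.3 says openly that the figures are one-tailed, and on that basis they reproduce. The mismatch does not inflate type I error, because the planned test is the stricter one. This stands, but it does not make the figure right for the planned analysis.
- **The overall ANCOVA is well powered.** At N = 75 the omnibus test has power 0.96 (f = 0.48) and 0.89 (f = 0.41), and 75 exceeds the stated 45 to 63. That is correct, but a significant overall test does not say which arm differs from Control. Section 6.3 itself powers those contrasts separately.
- **0.59 is the lowest of four values and assumes no covariate gain.** Both are true. Section 1.4 reports that the most inhibited pilot subjects improved most, so some correlation between pre-test and change is plausible. The plan gives no correlation, and does not say whether its pooled SD is already adjusted. The peak torque figures show no gain, so 0.59 stands as a conditional value.
- **The CAR inputs are unsettled.** Section 1.4 gives changes of 8.3% (WBV), 5.9% (LMV) and 0.7% (Control), while section 6.3 calls 8.26% and 5.86% differences from Control. It also puts LMV versus WBV at 0.68%, although 8.26 − 5.86 = 2.40. The CAR powers above inherit that doubt. The mismatch of tests does not depend on it.

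**Conclusion.** The concern holds. The 0.80 power stated for Aim 1 belongs to a more lenient test than the one planned. With the tabled effect sizes, 25 analysed per group and no covariate gain, three of the four comparisons fall below 0.80, and a true LMV effect on peak torque of the assumed size would be missed about 41% of the time (1 − 0.59). Even without the Dunnett adjustment, a two-sided t-test gives that comparison only 0.68. A pre-test correlation of about 0.60 with the change score would restore 0.80 for it; smaller correlations would do so for CAR. Section 6.3 states no allowance for dropout, and any loss of subjects lowers these values further.

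**What to change.** In section 6.3, replace the one-tailed power statement for Aim 1 with power for the analysis in section 6.2: two-sided Dunnett, overall 0.05, 25 per group. Without covariate gain the values are about 0.88 (WBV) and 0.59 (LMV) for peak torque, and 0.76 and 0.69 for CAR. If the pilot data give the R-squared of the pre-test for the change score, report it with the adjusted values, and say whether the tabled pooled SD is adjusted. Reconcile the CAR differences in sections 1.4 and 6.3 before fixing the CAR values.

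Remove 13 to 26 per group as the justification for Aim 1. If it is kept for the record, label it as one-tailed and unadjusted. Put the Aim 2 sample size on the two-sided basis of section 6.2 in the same edit.

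The cost is a rewording of section 6.3 and a less favourable stated power. Enrolment, design and the planned analysis can stay as they are.

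### The Aim 2 requirement of 194 is a one-tailed figure that fits CAR only, while the planned test is two-sided, and the claim that 75 subjects can show similarity has no calculation behind it

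*Combined protocol and SAP*

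**What the plan says.** Section 6.3 tables LMV-versus-WBV effect sizes of 0.36 for CAR ("CAR 0.84 0.78 0.36", third value) and 0.35 for peak torque. It states that power for these effects "was calculated for one-tailed independent t-tests". For Aim 1 it gives a range, "a sample of 39-78 subjects (13-26 per group) would provide statistical power of 0.80". For Aim 2 it gives one number, "194 subjects (97 per group) would be necessary to provide adequate power", and attaches it to the effects of both outcomes.

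It then argues that WBV-LMV differences are too small to matter (0.68% for CAR, 0.04 N/kg for peak torque), sets the sample at 75 (25 per group), and ends: "This sample size will provide adequate power to demonstrate similar improvements in quadriceps function with WBV and LMV".

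Section 6.2 says that the adjusted WBV-versus-LMV change scores "will be tested for the pairwise comparison of WBV versus LMV at the two-sided 0.05 significance level", in an ANCOVA with the pre-test value as covariate.

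**The concern.** The sample size in 6.3 and the test in 6.2 do not match. One is one-tailed and the other two-sided, and no directional hypothesis for Aim 2 would justify a single tail: section 1.4 expects similar effects, and section 1.3 calls the comparison unclear. A single figure for two different effect sizes can also fit only one of them.

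The larger risk is the closing sentence. The only Aim 2 analysis is a test of difference, and 6.3 never states its power at 25 per group. A reader told that the sample is adequate to show similarity may take a non-significant result as evidence of similarity. The synopsis lists the comparison as a primary objective, and section 6.3 makes quadriceps function the primary outcome. Section 1.3 contrasts a WBV device costing up to 10,000 dollars with an LMV device of about 250 dollars, so a conclusion of similarity could affect which device is taken forward.

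**Working it through.** **Inputs.** Effect sizes d = 0.36 (CAR) and 0.35 (peak torque), one-tailed basis, and 25 per group: section 6.3. Two-sided 0.05 test: section 6.2. Target power 0.80: stated in 6.3 for Aim 1. The Aim 2 sentence gives no number, but 0.80 reproduces its figure.

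**1. Reproduce 97 per group, then change the sidedness.** Two-sample t-test, equal groups, noncentrality d × √(n/2), alpha 0.05, power 0.80:

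| Outcome | d | One-tailed n per group | Two-sided n per group | Two-sided total |
|---|---|---|---|---|
| CAR | 0.36 | 96.1 → 97 | 122.1 → 123 | 246 |
| Peak torque | 0.35 | 101.6 → 102 | 129.1 → 130 | 260 |

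The stated 194 = 2 × 97 matches only the one-tailed CAR cell. Against the two-sided totals, 194/246 = 0.79 and 194/260 = 0.75.

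**2. Two-sided power, same method.** At 97 per group: 0.70 (CAR) and 0.68 (peak torque). At 25 per group: 0.24 and 0.23.

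**3. Allow for the covariate.** If the tabled effects are unadjusted, a within-group baseline-change correlation r raises d to d/√(1 − r²) and cuts n by a factor of about 1 − r². The documents give no r, so these values are assumptions:

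| r (assumed) | n per group, two-sided (CAR to peak torque) | Power at 25 per group (peak torque to CAR) |
|---|---|---|
| 0 | 123 to 130 | 0.23 to 0.24 |
| 0.3 | 112 to 118 | 0.25 to 0.26 |
| 0.5 | 92 to 98 | 0.29 to 0.30 |
| 0.6 | 79 to 83 | 0.33 to 0.34 |

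**4. Precision at 25 per group.** Error df = 75 − 3 − 1 = 71. The 95% CI half-width is 1.994 × √(2/25) = 0.56 SD before any covariate gain. At r = 0.6 it is 0.56 × √(1 − 0.36) = 0.45 SD. Both exceed 0.35 to 0.36.

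**5. Could the sample show similarity?** The plan sets no margin. As an illustration, take two one-sided 0.05 t-tests (df 48) and a true difference of zero. Power of 0.80 then needs a margin of about (1.677 + 1.299) × √(2/25) = 0.84 SD, as large as the tabled WBV-versus-Control effect on CAR (0.84).

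**6. Check the inputs against each other.** Section 6.3 gives differences from Control of 8.26% (WBV) and 5.86% (LMV) for CAR, and 0.29 and 0.20 N/kg for peak torque. These imply WBV-LMV gaps of 8.26 − 5.86 = 2.40% and 0.29 − 0.20 = 0.09 N/kg, not 0.68% and 0.04 N/kg. The SDs implied by the Control comparisons are 8.26/0.84 = 9.83 and 5.86/0.78 = 7.51 for CAR, and 0.29/0.98 = 0.296 and 0.20/0.70 = 0.286 for peak torque. On those SDs:

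- 0.68% is d = 0.07 to 0.09, and 2.40% is d = 0.24 to 0.32.
- 0.04 N/kg is d = 0.14, and 0.09 N/kg is d = 0.30 to 0.32.

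None reaches the tabled 0.36 or 0.35. One lead: section 1.4 reports within-group CAR changes of +8.3% (WBV), +5.9% (LMV) and +0.7% (Control), which match 8.26, 5.86 and 0.68 after rounding. Within-group changes may therefore have been labelled as differences in 6.3. The documents do not settle this.

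**The case against.** **The planned test is not an unadjusted t-test.** It is a baseline-adjusted contrast, and the documents lead one to expect some correlation: section 6.2 hypothesises larger gains in those with worse baseline function. A reader might infer that the planned test needs 246 to 260 outright. The documents do not support that. At an assumed r of 0.5 the two-sided need is 92 to 98 per group, close to the stated 97. This stands, and it makes 246 to 260 conditional. It does not rescue 6.3, which claims no such gain and presents a one-tailed t-test. Nor does it bring power at 25 per group anywhere near 0.80.

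**The shortfall is disclosed.** Section 6.3 states the one-tailed basis, says Aim 2 would need far more than 75 subjects, and argues that such a difference is unlikely to matter. A reader might infer that the trial claims to be powered for a WBV-LMV difference, or that enrolment must rise. Neither follows: 194 did not set the sample size, and a larger requirement only strengthens the stated reason for not powering Aim 2.

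**The inputs are themselves in doubt.** This also stands. If the stated 0.68% and 0.04 N/kg were right on the SDs implied above, the requirement would be far higher (roughly 800 to 3,280 per group by normal approximation). New figures should not go into the plan until this is resolved.

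None of these objections supports the closing sentence, which lacks a margin and an equivalence test whichever requirement is right.

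**Conclusion.** The point holds in conditional form. The 194 is a one-tailed figure for CAR alone and does not fit the two-sided test in 6.2. By the plan's own t-test method and tabled effects, the two-sided need is 246 to 260, so 194 is 21% to 25% short, and power at 25 per group is 0.23 to 0.24. This rests on target power of 0.80, effects of 0.36 and 0.35 taken as given, no covariate gain and no dropout. Assumed correlations of 0.3 to 0.6 would move it to about 79 to 118 per group and power of about 0.25 to 0.34.

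The sidedness and single-outcome errors are modest corrections to a number that did not set the sample. The more serious defect is the unsupported claim about showing similarity. With a confidence interval half-width of 0.45 to 0.56 SD over the range of r considered, a non-significant Aim 2 result would be compatible with differences larger than the planning effects.

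**What to change.** 1. Reconcile the LMV-versus-WBV effect sizes (0.36, 0.35) with the stated mean differences (0.68%, 0.04 N/kg) and with those implied by the Control comparisons (2.40%, 0.09 N/kg). Check whether 8.26, 5.86 and 0.68 are within-group changes. Say whether the pooled SD is baseline-adjusted.
2. Restate the Aim 2 requirement on a two-sided 0.05 basis for both outcomes: 246 to 260 in total if the tabled effects stand and no covariate gain is taken. If a gain is claimed, give the correlation and its source.
3. State the Aim 2 power at 25 per group (about 0.23 to 0.24 on that basis).
4. Delete the closing sentence on adequate power for similarity.
5. Report WBV minus LMV as an estimate with a 95% confidence interval, and state that non-significance will not be read as similarity.

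The cost is a return to the pilot data for step 1 and text changes in 6.2 and 6.3. The stated figures become less favourable. Enrolment and trial procedures do not change.
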